Function 4: Improve communication between patient and providers regarding intentions and goals for timely, guideline-adherent PORT.

Form: Standardized discussion of expected indication for PORT and choice of radiation facility at initial consultation. At the initial surgical consultation, the clinician informs the patient that based on his/her clinical stage, it is expected that treatment will include a package of surgery and PORT. At this same clinical encounter, the NDURE navigator facilitates a discussion with the patient and clinician to help the patient decide at which facility he/she will receive PORT.

Function 5: Enhance coordination of care between healthcare teams during care transitions and about treatment sequelae.

Form: NDURE PORT Care Plan. At each navigation encounter, the NDURE navigator meets with the patient, caregiver, and clinicians to generate (and update) a PORT Care Plan. The NDURE PORT Care Plan is an EMR-based document that (a) captures clinical factors and the care delivery processes necessary to start PORT; (b) describes the patient's barriers to timely PORT; and (c) documents the patient's personalized Barrier Reduction Plan.

Function 6: Restructure the organization to clarify roles and responsibilities for care processes associated with PORT delivery to avoid duplication and gaps in care.

Form: NDURE Navigator makes referrals and schedules appointments to optimize adherence with key PORT care delivery process. The NDURE navigator is assigned sole responsibility for making all PORT-related referrals (and scheduling appointments) with radiation and medical oncology, dentistry, and oral surgery in a manner that optimizes adherence to the following care delivery processes associated with timely PORT.

- (1) Prior to surgical resection, the patient has consultation with a radiation oncologist at the facility where the patient intends to receive PORT.
- (2) Prior to surgical resection, the patient has a consultation with a dentist and oral surgeon (if indicated) and subsequently undergoes extraction of indicated teeth at the time of surgical resection.
- (3) Engaging with the pathologist if the pathology report is not issued by postoperative day 8. Upon receipt of the pathology report, promptly communicating key pathologic findings to the HN team to facilitate formation of a plan for pathology-directed adjuvant therapy.

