8.4.6 CANCER CARE DELIVERY PROCESS ASSESSMENTS

A Cancer Care Delivery Process form is included as the eCRF and will be completed by the program coordinator using information from the EMR.

Pre-Surgical Radiation Consultation is defined as the attendance by the patient at a consultation with the treating radiation oncologist (at MUSC or elsewhere) prior to surgery to discuss RT in the definitive or adjuvant setting. Patients who see a radiation oncologist at one facility prior to surgery but receive PORT at a different facility are evaluated as 'no' for this measure.

Pre-Radiation Therapy Dental Evaluation is defined as the evaluation by a dentist for pre-radiation dental extractions. Edentulous patients are non-evaluable for this measure. Dentulous patients who do not have a pre-surgical dental evaluation are evaluated as 'no'.

Pre-Radiation Extractions of Indicated Teeth with Definitive Surgery is defined as the extraction of indicated carious/non-restorable teeth either prior to or during definitive surgery. Patients who have a dental evaluation that indicates the need for extractions, but for whom teeth are not extracted prior to or during

surgery are evaluated as 'no' for this measure. Edentulous patients and dentulous patients who have a dental evaluation and extractions are not recommended are not evaluable for this measure.

Time from Surgery to Pathology Report is defined as the production of the pathology report from the definitive surgical procedure within the EMR. Addenda to the pathology report at the request of the HNSCC team (e.g. tumor p16 status) are not counted in this measure.

Time from Surgery to PORT Referral is defined as the time, in days, from the date of the definitive surgical procedure to the date the referral (or postoperative appointment) is placed to discuss adjuvant therapy with the treating radiation oncologist. For patients who have seen a radiation oncologist prior to surgery, this metric refers to the scheduling of the post-operative follow-up appointment with the radiation oncologist. In situations in which a patient is re-referred postoperatively (i.e., a patient is referred to a radiation oncologist at one facility and then decides to get treatment at a different facility), the measure is evaluated using the time to the second referral.

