3. Have an indication for PORT per NCCN Guidelines based on the presence of at least one of the following adverse features on final pathologic evaluation: ENE, positive margin, pT3 or pT4 primary, at least pN1 nodal disease (per AJCC 8th edition for p16-ve non-oropharyngeal SCC or AJCC 7th edition for p16+ve oropharyngeal SCC), nodal disease in levels IV or V, PNI or LVI

Analysis will be performed based on assignment at randomization regardless of the intervention received (modified intent to treat). This analysis set will be used for analysis of the secondary endpoint TTP.

The **treatment package time (TPT) analysis set** is the TTP analysis set restricted to patients who have initiated PORT.

The **full analysis set (FAS)** is the set of all trial participants who enroll and are eligible for the study. Patients who enroll but subsequently drop out prior to receiving any of the assigned intervention will be replaced. The FAS will be used for evaluation of the pre-surgical radiation consultation, and for secondary analyses of both the primary endpoint and secondary endpoints.

The **dental evaluation prior to surgery analysis set** will be the FAS restricted to patients who receive curative intent surgery at MUSC and are indicated for dental evaluation.

The **extraction of indicated teeth analysis set** is the subset of patients in the dental evaluation prior to surgery analysis set who are indicated for dental extractions prior to surgery.

The **time from surgery to PORT referral scheduling analysis set** and **time from surgery to appointment with radiation oncology analysis set** are equivalent to the TTP analysis set.

The **Per protocol set** is composed of all patients enrolled in the trial who have completed all 3 of the ENDURE intervention sessions as described in the protocol. This analysis set will be used for secondary analyses of both the primary endpoint and secondary endpoints.

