Pre-surgical radiation consultation, NDURE vs UC: will be analyzed using a binary regression GLM with identity link as described. If the GLM fails to converge, then unadjusted (empirical) rates and corresponding 90% CIs will be constructed, with trial-arm comparisons conducted using a z-test of two independent proportions. Analyses will be performed using the FAS.

Dental evaluation prior to surgery, NDURE vs UC: will be analyzed using a binary regression GLM with identity link as described. If the GLM fails to converge, then unadjusted (empirical) rates and corresponding 90% CIs will be constructed, with trial-arm comparisons conducted using a z-test of two independent proportions. Analyses will be performed using the dental evaluation prior to surgery analysis set.

Extraction of indicated teeth, NDURE vs UC: will be analyzed using a binary regression GLM with identity link as described. If the GLM fails to converge, then unadjusted (empirical) rates and corresponding 90% CIs will be constructed, with trial-arm comparisons conducted using a z-test of two independent proportions. Analyses will be performed using the extraction of indicated teeth analysis set.

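### The extraction endpoint's denominator depends on a dental evaluation that NDURE is designed to bring about, and dentulous patients who are never evaluated have no scoring rule

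*Combined protocol and SAP*

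**What the plan says.** The plan has two dental measures for the RCT.

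**Extraction of indicated teeth.** Under Section 9.3 the analysis set "is the subset of patients in the dental evaluation prior to surgery analysis set who are indicated for dental extractions prior to surgery". Section 8.4.6 describes the failures: "Patients who have a dental evaluation that indicates the need for extractions, but for whom teeth are not extracted prior to or during" surgery. It then names those left out: "Edentulous patients and dentulous patients who have a dental evaluation and extractions are not recommended are not evaluable for this measure". Section 9.4.4.2 compares the arms on this measure: "Analyses will be performed using the extraction of indicated teeth analysis set".

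**Dental evaluation before surgery.** Section 9.3 says this set "will be the FAS restricted to patients who receive curative intent surgery at MUSC and are indicated for dental evaluation". Having had an evaluation is not a condition of membership. Section 8.4.6 adds: "Dentulous patients who do not have a pre-surgical dental evaluation are evaluated as 'no". Section 9.4.4.2 gives the measure its own comparison: "Dental evaluation prior to surgery, NDURE vs UC: will be analyzed using a binary regression GLM with identity link as described".

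The synopsis, the Schedule of Activities and Table 2 list the extraction measure. None of them lists the evaluation measure.

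Section 6.1.1.1 (Function 6) makes the navigator solely responsible for dental and oral surgery referrals. One of the care processes to be achieved is this: "Prior to surgical resection, the patient has a consultation with a dentist and oral surgeon (if indicated"), followed by removal of indicated teeth at the time of resection. Table 3 says usual care makes these referrals through a varying set of staff who do not specifically aim at these processes.

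**The concern.** A patient enters the extraction denominator through a recorded indication, and an indication normally requires a dental evaluation. That evaluation normally follows randomization, and raising its frequency is part of the intervention. Membership of the set is therefore likely to differ by arm for reasons tied to treatment. The evaluated usual-care patients may also be a selected group, so the comparison could be distorted in either direction as well as diluted.

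Section 9.3 defends post-randomization exclusions from the primary analysis set because they turn on facts that cannot be known at enrollment, such as final pathology or early death. That argument does not extend to a patient who is excluded because no dental referral was made.

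At stake is the reading of a listed secondary endpoint. A null result on extraction could arise although NDURE had raised the share of patients whose indicated teeth were out by surgery.

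**Working it through.** The plan states no expected rate, sample size or power for either dental measure, so there is no figure to reproduce. The check has two parts.

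**1. How each type of operated patient is scored (Sections 8.4.6 and 9.3)**

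| Patient | Evaluation measure | Extraction measure |
|---|---|---|
| Edentulous | not evaluable | not evaluable |
| Evaluated before surgery, no extraction recommended | yes | not evaluable |
| Evaluated before surgery, extraction indicated and done by surgery | yes | yes |
| Evaluated before surgery, extraction indicated, not done by surgery | yes | no |
| Dentulous, first evaluated after surgery, extraction indicated | no | no under 8.4.6; unclear under 9.3 |
| Dentulous, never evaluated | no | no rule given |

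The last two rows hold the problem. Section 8.4.6 sets no time limit on the evaluation that produces the indication. In Section 9.3 the words about timing may qualify either the finding or the extractions. Two analysts could build different denominators from the same data.

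The table also shows that the joint target in Function 6 is not estimated. A patient evaluated but not extracted is a success on evaluation, and a patient never evaluated is absent from extraction. Multiplying the two rates does not recover the joint outcome. The evaluation set includes patients who need no extraction, and the share with an indication may differ between arms that were evaluated selectively.

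**2. Possible size (all rates assumed)**

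Among patients who truly need extractions, let:
- e = probability of a dental evaluation before surgery;
- x = probability of extraction by surgery, given that evaluation;
- s = share of unevaluated patients who still enter the denominator, as failures, through a later evaluation (taken as equal in both arms).

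Observed extraction rate = e·x / [e + (1 − e)·s].

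Take x = 0.90 in both arms and e = 0.90 under NDURE.

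- s = 0 (all unevaluated dropped): the rate is x = 90% in both arms, so the difference is 0 for any usual-care e.
- s = 1 (all counted as failures): NDURE = 0.90 × 0.90 = 81%; usual care = e × 0.90.
- s = 0.5: NDURE = 0.81 / 0.95 = 85.3%. With usual-care e = 0.40, the rate is 0.36 / 0.70 = 51.4%.

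| Usual-care e | Usual-care rate, s = 1 | Difference, s = 1 | Difference, s = 0.5 | Difference, s = 0 |
|---|---|---|---|---|
| 40% | 36% | 45 points | 34 points | 0 |
| 60% | 54% | 27 points | 18 points | 0 |
| 80% | 72% | 9 points | 5 points | 0 |
| 90% | 81% | 0 | 0 | 0 |

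The hidden amount is the s = 1 column minus the difference actually shown. If all unevaluated patients are dropped, it is 45, 27, 9 or 0 points. If half are captured later, it is about 45 − 34 = 11, 27 − 18 = 9, 9 − 5 = 4, or 0 points.

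**The case against.** A reader might infer that usual-care patients who never see a dentist are certain to leave the denominator, and that the failure NDURE targets then vanishes from the trial. The documents do not support that.

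- The failure is still counted. Dentulous patients without a pre-surgical evaluation score as failures on the evaluation measure, which has its own set and its own risk-difference analysis. With evaluation at 90% versus 40%, that measure would show 50 points.
- Exclusion from the extraction set is inferred from silence. The list of non-evaluable patients does not name the never-evaluated, and a patient first evaluated after surgery can be scored as a failure under Section 8.4.6.
- The zero difference is a worst case. It needs every unevaluated patient dropped and equal extraction given evaluation, although NDURE acts on extraction too. With x = 90% versus 80%, the measure as written would show 10 points.
- A composite may add little. If n is the share of evaluated patients needing extraction, its difference in the 90% versus 40% case is (0.90 − 0.40) × (1 − 0.1n), or 45 to 50 points, against 50 on evaluation alone.

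These points limit the concern but do not remove it. The evaluation measure is missing from every endpoint list, the joint target goes unestimated, and the extraction comparison still conditions on a step the intervention changes. Section 9.3 also names the full analysis set for secondary analyses of secondary endpoints, but without a score for the unevaluated this does not help.

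**Conclusion.** The concern holds in limited form. The between-arm extraction comparison is not protected by randomization. Dentulous patients who are never evaluated have no scoring rule, and they probably drop out more often under usual care. The comparison can therefore miss or distort NDURE's effect on a listed secondary endpoint.

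The size cannot be known from the documents. The range of 0 to 45 hidden points rests on assumed evaluation and extraction rates and on dropping every unevaluated patient. It shrinks as usual-care evaluation approaches the NDURE rate, or as more patients are captured by later evaluation.

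This is a secondary process measure in a pilot, so the text should be changed, but the primary analysis of PORT delay is untouched.

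**What to change.** 1. Add to Section 9.4.4.2 a between-arm comparison of *dental clearance by definitive surgery* in the existing dental evaluation prior to surgery analysis set. Yes = evaluated before surgery, and either no extraction indicated or all indicated teeth extracted before or during surgery. No = otherwise, including dentulous patients who were not evaluated.
2. Report the evaluation rate and the extraction rate given an indication beside it, by arm. State that the second is conditional on a post-randomization step. It need not be reduced to a descriptive figure.
3. Align Sections 8.4.6 and 9.3 on whether the evaluation must precede surgery, and state how never-evaluated dentulous patients are handled in the extraction measure.

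The cost is wording in Sections 8.4.6, 9.3 and 9.4.4.2. The component measures are already defined for the Cancer Care Delivery Process form, and no new visit is needed. The downside is that the composite mixes two steps and may be driven mainly by evaluation, which is why the components must be shown. Its set still conditions on surgery at the site, but no longer on who was evaluated.

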9.4 STATISTICAL ANALYSES

9.4.1 GENERAL APPROACH

We will construct graphical displays and calculate descriptive statistics (e.g. frequencies and percent for categorical variables, and mean, median, standard deviation, and range for continuous variables). For inferential tests, we will use a p-value of 0.05, two-sided, and 90% confidence intervals (CIs) to assess statistical significance (Type I error), unless otherwise noted. Covariates included in the analysis plan will be pre-specified as described below. Normality of the data will be assessed before statistical procedures will be performed. We will evaluate variable transformations as needed to satisfy assumptions and consider transformations of variables to induce approximate normality and stabilize variance as needed. Nonparametric tests will be applied when appropriate.

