4.2 RCT OF NDURE VERSUS USUAL CARE

4.2.1 OVERALL DESIGN

We will conduct a single-site, non-blinded, parallel-group, RCT of NDURE versus usual care for the management of delays and racial disparities starting PORT in adults with surgically-managed, locally advanced HNSCC. The study is designed to test the following hypotheses: 1) NDURE will result in a lower rate of delayed PORT relative to usual care (primary objective) and 2) NDURE will result in a smaller difference in PORT delay between AA and whites relative to usual care (secondary objective). The statistical plan for this between-group design analyzes the superiority of NDURE relative to usual care, although our power analysis is calculated with $\alpha = 0.1$ and $1 - \beta = 0.8$ based on the desire to emphasize power over type I error at this early stage of development (single-site pilot RCT) to ensure follow-up on promising interventions.

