9.2.2 RCT OF NDURE VERSUS USUAL CARE

Power and sample size calculations were performed using PASS v08.0.13, “Inequality Tests for Two Independent Proportions.” The primary endpoint for this pilot RCT is the rate of PORT delay, defined as starting PORT > 6 weeks after surgery. Our primary objective is to compare PORT delay rates between the NDURE and usual care arms. We hypothesize that, compared with patients who receive usual care, patients who receive NDURE will have a decreased rate of PORT delay (initiation of PORT > 6 weeks after surgery). Alternatively, our null hypothesis is that there will be no difference in the rate of PORT delay between NDURE and usual care. We assume the rate of PORT delay in the usual care arm will be 45%⁴⁵ and target an absolute reduction in PORT delay of 20% (rate of PORT delay in the NDURE arm = 25%)²⁴. This effect size is clinically significant and realistic given results in similar (non-randomized) interventions²⁴. Seventy-five patients in each arm yields 83% power to detect a 20% reduction in PORT delay (45% versus 25%) based on a two-sided Z-test with pooled variance of two independent proportions assuming a two-sided $\alpha = 0.1$. Our selection of $\alpha = 0.1$ and $1 - \beta = 0.8$ is based on the desire to emphasize power over type I error at this early stage of development (single-site pilot RCT) to ensure follow-up on promising interventions. Furthermore, given the trial’s design, comparison of PORT delay rates between

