trial arms will be analyzed using a model-based approach (discussed in Section 9.4.3.2) with inclusion of randomization stratification variables as model covariates, an analytic approach which preserves the type I error rate at nominal α , and increases power relative to an unadjusted model.⁶¹ Therefore, our power analysis based on a Z-test is conservative, and we anticipate even greater power based on our analytic plan. We therefore consider our RCT to be appropriately and rigorously designed to detect a clinically meaningful reduction in PORT delay. In order to have 150 patients eligible for the PORT delay analysis set (see Section 9.3, Population for Analyses), we plan to enroll 170 patients. Our sample size is inflated by 17% based on historical data. If at 170 patient accruals we have not achieved 75 patients evaluable for the primary endpoint in each arm, we will continue to enroll until we have achieved either accrual of a minimum of 75 evaluable patients in each arm or have accrued a maximum of 180 total patients.

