9.4.3.2 RCT OF NDURE VERSUS USUAL CARE

For the primary endpoint (delays starting PORT as defined in **Section 8.4, Endpoint and Other Non-Safety Assessments**), the difference in PORT delay comparing NDURE to UC will be evaluated using a model-based approach to accommodate adjustment for randomization stratification variables. Specifically, we will use a binary regression generalized linear model (GLM) with identity link to model the probability of PORT delay as a function of treatment arm and randomization stratification variables (race and predicted location of radiation facility). We adopt this approach as opposed to a logit model or Mantel-Haenzel (MH) type approach since the estimand is the population average treatment effect, whereas the odds ratio is not collapsable and therefore inference based on logistic regression or MH estimation would be limited to a conditional treatment effect. (Additional details can be found in the FDA Guidance Document on Adjusting for Covariates in Randomized Clinical Trials.) The risk difference (PORT delay rate in UC – PORT delay rate in NDURE) will be estimated based on the treatment effect slope parameter. We will report the corresponding model-based 90% CI and two-sided p-value. We will additionally report model-based PORT delay rates for each trial arm with corresponding 90% CIs. Should GLM convergence be an issue, we will adopt an alternative approach based on subject-level predicted probabilities of PORT delay from a logistic model as outlined by Freedman⁶² and by Steingrimsson.⁶³ Analysis will be performed using the PORT delay analysis set.

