9.4.4.2 RCT OF NDURE VERSUS USUAL CARE

PORT delay disparity (Black vs White) in NDURE vs UC: The comparison of PORT delay disparity (PORT delay in Black patients vs PORT delay in White patients) in NDURE versus UC will be evaluated using a similar GLM as described for the primary endpoint, but the model will include a race-by-treatment

arm interaction term. Model-based estimates of PORT delay disparity will be constructed for each arm with corresponding 90% CIs. The model-based difference in disparity between trial arms will be reported along with corresponding 90% CIs. Analysis will be performed using the PORT delay analysis set.

Time-to-PORT initiation, NDURE vs UC: TTP will be analyzed using cumulative incidence plots (1 – Kaplan-Meier plots) with Greenwood variance estimation to construct corresponding 90% CIs. Treatment group comparisons will be conducted using a stratified log-rank test adjusting for randomization stratification variables. As noted, TTP will be right-censored for evaluable patients who die or are lost to follow-up prior to PORT initiation, or who haven't received PORT by the end of follow-up (18 weeks post-operatively). The hazard ratio comparing the two arms will be estimated using Cox proportional hazards regression controlling for stratification variables. A sensitivity analysis will be conducted treating deaths prior to PORT initiation as a competing risk to evaluate the bias incurred in cumulative incidence estimation by right-censoring deaths. Analyses will be performed using the TTP analysis set.

Time-to-PORT initiation (Black vs White) in NDURE vs UC: TTP cumulative incidence plots (1 – Kaplan-Meier plots) will be constructed for Black and White patients randomized to NDURE and for Black and White patients randomized to UC as described. Group comparisons will be conducted using a stratified log-rank test, but controlling only for predicted radiation facility as a randomization stratification variable since a race-by-trial arm interaction term is used to evaluate this hypothesis. A Cox proportional hazards regression model will be fit as described with appropriate race-by-trial arm interaction. Censoring rules will be as described in Section 9.4.2. A sensitivity analysis will be performed treating deaths prior to PORT initiation as a competing risk. Analyses will be conducted using the TTP analysis set.

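### Section 9.4.1 pairs a two-sided p-value of 0.05 with 90% CIs as one significance criterion; the two disagree for p between 0.05 and 0.10, and the primary analysis names no threshold

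*Combined protocol and SAP*

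**What the plan says.** Section 9.4.1 (General Approach) gives the default for all inferential tests: "we will use a p-value of 0.05, two-sided, and 90% confidence intervals (CIs) to assess statistical significance (Type I error), unless otherwise noted". Both the p-value and the interval are given the task of judging significance.

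The other sections that bear on the level are these:

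- **4.2.1 (Overall Design)** uses alpha 0.1 with 80% power and explains the choice by "the desire to emphasize power over type I error at this early stage of development (single-site pilot RCT) to ensure follow-up on promising interventions".
- **9.2.2 (Sample Size, RCT)** repeats that alpha, states it as two-sided, and reports 83% power with 75 patients per arm for 45% versus 25% PORT delay, using a pooled-variance Z-test. It then describes the covariate-adjusted primary model as "an analytic approach which preserves the type I error rate at nominal" alpha.
- **9.4.3.2 (primary analysis, RCT)**: "We will report the corresponding model-based 90% CI and two-sided p-value". It gives no significance level and no success criterion.
- **9.4.4.2 (secondary analyses, RCT)**, on the difference in racial disparity between arms: "The model-based difference in disparity between trial arms will be reported along with corresponding 90% CIs". It mentions no p-value for that contrast. No alpha is given for this or any other secondary test.

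**The concern.** A two-sided test at 0.05 pairs with a 95% CI, and a 90% CI pairs with a two-sided test at 0.10. One sentence therefore holds two rules. They agree when p is below 0.05 or is 0.10 or above, and contradict each other in between. A one-sided 0.05 would reconcile them, but the sentence says two-sided. Treating the 90% CI as purely descriptive would also reconcile them, but the sentence assigns it to the assessment of significance.

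If the primary p-value fell in that range, the 90% CI would exclude zero and support a claim of benefit, while the literal p-value rule would deny it. Reporting estimate, interval and p-value together lets a reader apply either rule. It does not fix the trial's own rule in advance, which matters more in a trial that is not blinded.

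The literal 0.05 rule would also judge the primary result by a test for which the trial was not sized.

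**Working it through.** **Inputs.** Section 9.2.2 gives delay of 45% in usual care and 25% in NDURE, 75 evaluable patients per arm, a pooled-variance Z-test, two-sided alpha 0.1 and stated power of 83%. Section 9.4.1 gives the alternative threshold of 0.05.

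**1. Reproduce the stated power.** The mean rate is (0.45 + 0.25)/2 = 0.35.

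- SE under the null: √(2 × 0.35 × 0.65 / 75) = 0.0779
- SE under the alternative: √((0.45 × 0.55 + 0.25 × 0.75) / 75) = 0.0762
- Power = Φ((0.20 − z × SE null) / SE alternative)

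| Two-sided level | z | Power, formula | Power, exact enumeration |
|---|---|---|---|
| 0.10 | 1.645 | 82.7% | 83.4% |
| 0.05 | 1.960 | 73.3% | 73.5% |

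The stated 83% is reproduced at two-sided 0.10 and not at two-sided 0.05.

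**2. How often the rules conflict.** I enumerated all pairs of binomial counts with 75 per arm and summed the probability that the pooled Z-test gives 0.05 ≤ p < 0.10.

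- 45% versus 25%: 9.8%
- 45% in both arms: 4.4%
- 35% in both arms: 5.5%

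**3. Worked example.** Take 34/75 delayed in usual care and consider results that favour NDURE. P-values come from the pooled Z-test and intervals from the unpooled SE.

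| NDURE delayed | Difference (points) | p | 90% CI (points) | 90% CI rule | 0.05 rule |
|---|---|---|---|---|---|
| 22/75 | 16.0 | 0.043 | 3.2 to 28.8 | significant | significant |
| 23/75 | 14.7 | 0.064 | 1.8 to 27.6 | significant | not significant |
| 24/75 | 13.3 | 0.094 | 0.4 to 26.3 | significant | not significant |
| 25/75 | 12.0 | 0.13 | −1.0 to 25.0 | not significant | not significant |

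At 23/75 the 95% CI runs from −0.7 to 30.0 points, which confirms that the 0.05 rule goes the other way. Because the test is two-sided, conflicts also arise when NDURE does worse. At 45/75, for instance, p = 0.072.

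**4. Which level the sections support.**

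| Section | Level indicated | Role |
|---|---|---|
| 4.2.1 | 0.1 | power calculation, with rationale |
| 9.2.2 | two-sided 0.1 | power calculation; model said to hold nominal alpha |
| 9.4.1 | two-sided 0.05 and 90% CI | default for inferential tests |
| 9.4.3.2 | 90% CI, p-value without threshold | primary analysis |
| 9.4.4.2 | 90% CI, no alpha | secondary analyses |

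The 0.05 is the outlier, but no section says that 0.10 is the decision threshold or that it replaces the default.

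**The case against.** The strongest reply is that the primary rule can be recovered. The 0.1 is stated and justified in 4.2.1 and 9.2.2. The model-based analysis is tied to nominal alpha, and 0.1 is the only alpha in that section. Every CI level given in 9.4 is 90%, and 9.4.1 yields wherever something else is noted. On this view the 0.05 is leftover wording.

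Most of that stands. A reader might infer that the primary verdict is wholly open to choice once the data are seen. The documents do not support that reading, because the weight of the plan is on 0.10. What survives is narrower: the 0.1 is stated as a basis for power, 9.4.3.2 does not repeat it, and the only p-value threshold in the analysis section contradicts it. Inferred intent is not a prespecified rule.

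A reader might also infer that the disparity difference carries the same explicit conflict. It does not. Section 9.4.4.2 asks there only for estimates with 90% CIs. Section 9.1.2 does set a null hypothesis for it, but a 0.05 criterion enters only through the 9.4.1 default.

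Nor do the documents show that 0.10 was meant for every test. The rationale for 0.1 concerns the primary power calculation and does not reach secondary, subgroup or exploratory tests.

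**Conclusion.** The contradiction in 9.4.1 is real and should be corrected before analysis. For the primary endpoint the intended level is very probably two-sided 0.10. The fault is that the default says otherwise and 9.4.3.2 does not settle it. For the secondary tests no alpha is stated, so the contradictory default is all there is.

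At the planned effect, about one trial in ten would fall where the two rules disagree. With no true difference the figure is 4 to 6%. These figures rest on the unadjusted pooled Z-test with exactly 75 evaluable patients per arm. Covariate adjustment may change them, by an amount the documents do not give.

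A reader might take the 73.3% to mean that the trial is underpowered. It does not: the sample size is correct at the alpha the plan chose. The lower figure applies only if two-sided 0.05 is really the intended test.

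**What to change.** 1. In 9.4.1, replace the 0.05 with a two-sided significance level of 0.10 for the primary endpoint, in line with 9.2.2 and the planned 90% CIs.
2. State that threshold in 9.4.3.2 beside the CI and p-value.
3. For secondary, subgroup and exploratory tests (9.4.4.2, 9.4.7 and 9.4.9), state one level and the CI that matches it: either 0.10 with the 90% CIs already planned, or 0.05 with 95% CIs. The sponsor should make this choice openly, since the existing rationale covers only the primary endpoint.
4. If the sponsor does intend 0.05 for the primary test, use 95% CIs there, restate alpha in 4.2.1 and 9.2.2, and restate the Z-test power as about 73%, below the 80% target.

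Keeping 0.10 for the primary endpoint costs one phrase in 9.4.1 and a clause in 9.4.3.2, plus a sentence on the level for the other tests. The sample size, the data collected and the planned 90% intervals for the primary endpoint do not change.
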